5.4 Population

The population to be enrolled in this clinical investigation comprises both male and female patients with severe symptomatic aortic stenosis (AS) who meet specific eligibility criteria defined within this document. The total population to be enrolled in the clinical investigation is at least 866 for COHORT A, added up with any additional patient enrolled in COHORT B, to a maximum of 1046 patients in total.

Cohort A: Patients enrolled directly into the Portico I study.

Cohort B: Patients implanted in previous SJM-sponsored regulatory (pre-market) investigations and first-in-human trials whom consent for ongoing follow-up in the Portico I study after the completion of their participation in the initial study. This population has the same underlying disease as the target population of this clinical investigation; that is severe symptomatic aortic stenosis.

The expected duration of participation in this clinical investigation of patients in Cohort A will be 5 years from the date of implant. For Cohort B, the expected duration of participation in this clinical investigation will be a maximum of 4 years, depending on their inclusion time post-implant.

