6.2 Clinical investigation activities and visits

Table 2 : List of clinical investigation activities and visits

Study activities and visits	En/Bas*	Imp*	P-Dis*	30 d*	1 Y*	2 Y	3 Y	4 Y	5 Y
Visit window	-6m-0**	0	0-7d	-7d+14d	±90d	±90d	±90d	±90d	±90d
Informed Consent	X								
Patient's eligibility assessment	X								
Angiography	X								
Demographics	X								
Medical and Cardiovascular History	X								
Native aortic valve assessment	X								
Access site assessment	X								
Surgical risk assessment	X								
Frailty assessment:									
- 5 meters walking time	X			X	X				
- Grip strength	X			X	X				
- Wasting and malnutrition parameters	X			X	X				
- Cognitive impairment or dementia (MMSE)	X			X	X				
Blood sample:									
- Serum Albumin (Frailty assessment)	X			X	X				
- Hemoglobin, Creatinine (if available)	X		X	X	X				
- Troponin	X		X ^a	X	X				
Physical assessment	X		X	X	X	X	X	X	X
12 lead ECG	X		X ^b	X	X				
Paced rhythm assessment ^f				(X)					
Medication assessment	X	X	X	X	X	X	X	X	X

Clinical Investigation Plan – PORTICO I

Echocardiography	X	X ^c	X	X	X	X	X	X	X
NYHA Classification	X		X	X	X	X	X	X	X
QoL questionnaire (EQ-5D)	X ^d		X	X	X				
The six-minute walking test	X			X	X	X	X	X	X
Modified Rankin Scale ^e	X		X	X	X				
Adverse Events Assessment	X	X	X	X	X	X	X	X	X
Device Deficiency Assessment	X	X	X	X	X	X	X	X	X
Resources utilization		X	X						

(X) as applicable

* For Cohort B, the informed consent and eligibility assessment will be conducted but all the other above mentioned data up to 1 year will not be re-collected (equivalent to grey background). Depending on time point of informed consent signed, the patient will enter the Portico I study at 1Y or later.

** For Cohort A, tests to confirm baseline measurements (e.g. Angio, CT, echocardiogram) should be within 6 months of index procedure.

^a Blood Sample for Troponin to be obtained between day 2 and 4 post-implant or at discharge whatever occurs first.

^b ECG within 24 hrs Post-implant AND at discharge but no later than 7 days Post-implant-whatever occurs first.

^c Assess aortic regurgitation with TEE if available or via fluoroscopy/angiography

^d The QoL questionnaire should be completed by the patient the closest possible to the implant date

^e The Modified Rankin scale should be completed additionally (if possible) 90 days after any neurological event (stroke, TIA, encephalopathy).

^f The permanent paced rhythm assessment is performed only if applicable

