6.2.1. Enrollment Visit

For the patients who participated in a SJM-sponsored regulatory or first-in-human trial, the enrollment will occur retrospectively (after the date they received their Portico Valve). The historical data collected through 1 year in those trials will not need to be re-collected for this clinical investigation.

For patients indicated for implantation of a new Portico Valve, the enrollment will occur prospectively (before the date they will receive their Portico Valve) at a maximum of 45 days prior to the date of the Portico Valve implant and no later than the date of the Portico Valve implant but before the implant takes place.

The following enrollment activities are performed after the patient has been screened and must occur before any investigational procedure/visit.

- The principal or delegated site personnel is responsible for screening all potential patients to determine patient eligibility for the investigation
- If a patient meets all pre-procedural inclusion criteria and does not meet any of the pre-procedural exclusion criteria, he/she is eligible for the investigation.
 - Inform the eligible patient verbally about the investigation and provide the information sheet and consent to the patient.
 - Provide ample time for the patient to read and understand the information sheet and consent and to consider participation in the clinical investigation. Invite the patient to ask questions if needed.
 - Obtain the signature and date hand-written from the eligible patient on the EC approved informed consent (If an eligible patient does not sign and date the informed consent, he cannot participate in the investigation. No further protocol required activities are performed)
 - Obtain the signature and date from the principal or delegated investigator who obtained consent on the EC approved consent
 - Provide one copy of the signed and dated version of the informed consent to the patient (signed by both patient and investigator)
 - File the original signed and dated version of the informed consent in the Investigator Site Binder (ISB).
- Record enrollment information (name of the investigation, date of consent and Inclusion/exclusion information) in the hospital records and complete the Enrollment form preferably within 5 days after enrollment (failure to meet this timeline will not be considered a protocol deviation)
- Notify the sponsor by submitting the enrollment form.

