9.2 Sample size estimation

9.2.1 Cohort A

The sample size estimation is based on the primary endpoint of this study, all-cause mortality at 1 year post implant for patients having received a Portico Valve.

It is assumed that the expected mortality rate at 1 year post implant will be 22.1% ²⁰), and the total recruitment period will be 2 years; at least 608 patients are required to be at risk at 1 year post implant, in order to establish a two sided 95% confidence limit (18.8%, 25.4%) using non-parametric survival analysis with Peto's variance²¹. With a dropout rate of 10%, at least 866 patients need to be recruited.

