9.4 Secondary endpoint analysis

The secondary endpoint analysis will include both cohorts but results will be presented separately.

All safety secondary endpoints will be estimated using non-parametric survival analysis, and the data will be presented with the aid of Kaplan-Meier curve. The time to event will be defined as from the implant date to the first occurrence of the event for the patients who experienced the event, or to the last documented contact date for the patients without the event.

All safety secondary endpoints will be reported at 30 days, 1 year, 2 years, 3 years, 4 years and 5 years post implant, as recommended by VARC 2.

Note: Safety events which occurred prior to the index procedure will be reported separately and will not be included in the safety secondary endpoints reporting.

All continuous secondary endpoints will be summarized with the number of non-missing data, mean \pm standard deviation, median and range (minimum – maximum).

All categorical secondary endpoints will be tabulated with number of occurrence, and the percentage.

Generalized linear mixed model will be used to assess the evolution of the NYHA class at baseline, 30 days, 1 year, 2 years, 3 years, 4 years and 5 years post implant.

General linear mixed model will be used to evaluate the improvement for the QOL at baseline, 30 days, 1 year, 2 years, 3 years, 4 years and 5 years post implant.

Other secondary endpoints analysis will be described in a separate statistical analysis plan. This document will be available upon request.

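### Cohort B must survive about a year or more to enrol, yet section 9.4 times its mortality from implant, so early rates are near 0% and later rates too low.

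*Combined protocol and SAP*

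**What the plan says.** Section 5.4 defines Cohort B as patients implanted in earlier sponsor trials "whom consent for ongoing follow-up in the Portico I study after the completion of their participation in the initial study". Their participation lasts "a maximum of 4 years, depending on their inclusion time post-implant". Under section 5.8, sites contact the earlier participants and invite them. The footnote to Table 2 in section 6.2 adds: "Depending on time point of informed consent signed, the patient will enter the Portico I study at 1Y or later". Data collection starts after consent (section 6.1.2), and section 6.2.1 states: "The historical data collected through 1 year in those trials will not need to be re-collected for this clinical investigation".

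On analysis, section 9.4 says "The secondary endpoint analysis will include both cohorts but results will be presented separately". For the safety endpoints, which in section 5.3.2 include all-cause and cardiovascular mortality, it uses Kaplan-Meier methods: "The time to event will be defined as from the implant date to the first occurrence of the event". It continues: "All safety secondary endpoints will be reported at 30 days, 1 year, 2 years, 3 years, 4 years and 5 years post implant". No exception is made for Cohort B. Delayed entry, a landmark or a conditional label appears neither there nor in section 9.1.

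**The concern.** Being alive at consent is a condition of membership in Cohort B. Two separate errors follow for all-cause and cardiovascular mortality.

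- **Labelling.** Cohort B can only estimate mortality among patients alive at about 1 year. Section 9.4 would report it as mortality from implant, with first-year deaths left out. No method applied to Cohort B alone can restore them.
- **Immortal time.** A patient who consents after year 1 is counted as at risk between year 1 and consent, when a death could not have been observed. This lowers even the conditional estimate. Delayed entry corrects it.

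For stroke and myocardial infarction, the size and direction of any error cannot be determined from the documents. They depend on whether first-year events from the earlier trials are linked, and on how closely the event is tied to early death.

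Long-term safety is the secondary objective (section 5.2.2), and Cohort B, about 180 patients (section 9.2.2), gets its own results. Section 9.5 allows interim reporting of secondary endpoints and, for reimbursement, of relevant data. A near-zero 1-year mortality that has nothing to do with the device could therefore reach outside readers.

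**Working it through.** **The plan's own figures.** The documents give no mortality figure for Cohort B. The only anchor is the Cohort A planning value in section 9.2.1, 22.1% at 1 year (survival 0.779). It reproduces: 1.96 × √(0.779 × 0.221 / 608) = 0.033, which gives 18.8% to 25.4% as stated; 608 / (0.779 × 0.9) = 867, against the stated 866.

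**Assumptions.** First-year mortality in Cohort B equals 22.1%. After that, mortality is a constant m per year, with m = 8%, 10% or 15%. Consent is at exactly 1 year, or intended consent is spread evenly over years 1-2 or 1-3. None of these is given in the documents for Cohort B.

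**Formulas, at year y.**

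- All implanted: 1 − 0.779 × (1−m)^(y−1).
- Conditional on being alive at 1 year, which is also the delayed-entry target: 1 − (1−m)^(y−1).
- As written: for intended consent time E, a patient enrols only if alive at E (weight (1−m)^(E−1)). Mortality is the weighted mean over E of 1 − (1−m)^(y−E), counted as zero where E ≥ y.

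**Worked case, m = 10%, consent over years 1-2.** The sum of weights is (1 − 0.9)/(−ln 0.9) = 0.949. At 2 years: (0.949 − 0.9)/0.949 = 5.2%, against a conditional value of 10.0%. At 5 years: (0.949 − 0.9⁴)/0.949 = (0.949 − 0.656)/0.949 = 30.9%, against 34.4%.

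| Mortality (%) at m = 8 / 10 / 15% | 2 years | 5 years |
|---|---|---|
| All implanted | 28.3 / 29.9 / 33.8 | 44.2 / 48.9 / 59.3 |
| Conditional on alive at 1 year | 8.0 / 10.0 / 15.0 | 28.4 / 34.4 / 47.8 |
| As written, consent over 1-2 years | 4.1 / 5.2 / 7.9 | 25.3 / 30.9 / 43.4 |
| As written, consent over 1-3 years | 2.1 / 2.7 / 4.3 | 22.2 / 27.2 / 38.9 |

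**Labelling gap** (row 1 minus row 2): 19-20 points at 2 years and 12-16 at 5 years. If mortality stayed at 22.1% a year, the gaps would be 17 and 8 points.

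**Immortal-time error** (row 2 minus row 3 or 4): 4-7 points at 2 years and 3-4 at 5 years for consent over years 1-2; 6-11 and 6-9 points for years 1-3. It is zero if everyone consents at exactly 1 year.

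**Does delayed entry work?** In simulations of 400,000 patients per scenario, delayed-entry Kaplan-Meier returned the conditional values within 0.3 points at m = 10%, and within about 0.5 points at m = 15%.

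**Early rates.** Since entry is at 1 year or later, 30-day mortality is 0% and 1-year mortality about 0%. If the ±90-day window in the 1-year column of Table 2 applied and every patient entered at day 275, 1-year mortality would be 1 − 0.9^(90/365) = 2.6% at 10% a year, or 1 − 0.779^(90/365) = 6.0% at 22.1% a year. These figures are illustrative only.

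**Missing deaths.** If 180 survivors enrol after 22.1% first-year mortality, 180 / 0.779 = 231 patients were implanted, and about 51 deaths are absent from the curve.

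**The case against.** The strongest reply is that the schedule already treats early Cohort B data as outside this study. Data up to 1 year are not re-collected, adverse events are assessed from the 1-year visit onward (Table 3), and the 30-day and 1-year visits are headed as Cohort A only (sections 6.2.5 and 6.2.6). An analyst might therefore show early Cohort B rates as not available. The definition of Cohort B is open, results are separate, no hypothesis test uses it, and the labelling error could be cured with a footnote. That is a fair reading of the schedule, but section 9.4 fixes the time origin and reporting times without exception, and it defers only other secondary endpoints to a separate SAP. The footnote would also leave the immortal-time error in place.

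A second objection is that delayed entry buys little at this sample size. With 180 patients, 10% a year and consent over years 1-2, root-mean-square error against the conditional target is 5.1 points as written and 5.3 with delayed entry at 2 years, and 4.9 for both at 5 years. With consent over years 1-3, delayed entry is better: 6.5 against 7.4 points at 2 years, and 5.7 against 7.9 at 5 years. The trade-off is real, but equal total error does not justify a biased curve whose error bars are too narrow.

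Three limits stand. The sizes rest on assumed mortality and consent timing. The ±90-day window belongs to the Portico I visit schedule and may not describe when Cohort B patients left the earlier trials. Linking earlier-trial records of consenting patients would add no deaths, because all of them survived to consent.

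**Conclusion.** The concern holds, and section 9.4 should be changed. The near-zero early mortality follows from who can enrol and needs no numerical assumption. Nor does the omission of first-year deaths from later rates. The immortal-time error always lowers the estimate, but it exists only if consent times vary, which the plan itself expects.

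The sizes are conditional on the 22.1% planning value carrying over to Cohort B, on 8-15% a year afterwards, and on the assumed spread of consent. The damage is confined to Cohort B mortality. Cohort A results are separate, and section 9.3 restricts the primary analysis to Cohort A. No direction is claimed for non-fatal events.

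**What to change.** In section 9.4, for Cohort B:

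- **All-cause and cardiovascular mortality.** Use Kaplan-Meier with delayed entry at the post-implant day of consent to Portico I. Report from a 1-year landmark, labelled *conditional on being alive at 1 year*, with numbers at risk. If everyone consents at 1 year, this is simply the landmark estimate.
- **30-day and 1-year mortality.** Do not report these from Cohort B, or take them from the full implanted cohorts of the earlier trials.
- **Non-fatal endpoints.** Label the rates as among survivors who consented. State whether earlier-trial events are linked, and omit the 30-day and 1-year rates if they are not. State from which day each patient counts as at risk. Keep the events between earlier-trial exit and consent that sections 6.1.2 and 6.2.1 require.
- **Assumption.** State that delayed entry assumes the timing of consent is unrelated to prognosis.

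The cost is one entry-time variable (consent date minus implant date) and table footnotes. The implant form does not apply to Cohort B (Table 3), so implant dates must come from the earlier trials. Precision falls where early risk sets are small. Simulated with 180 patients at 10% a year, the standard error at 2 years rises from 1.6 to 5.3 points (consent over years 1-2) or from 1.2 to 6.8 (years 1-3). At 5 years it rises from 3.4 to 4.9, or from 3.3 to 5.9. No new visits or patients are needed.

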5.3.2 Secondary Endpoints

- Evaluation of the VARC-2¹⁹ defined event rates at 30 days, 1 year and annually through 5 years post implant. Definitions are detailed in Appendix D: VARC 2 Endpoints Definitions.
 - All-Cause Mortality
 - Cardiovascular Mortality
 - Myocardial Infarction
 - Stroke (disabling and non-disabling)
 - New or worsened conduction disturbances and cardiac arrhythmias (including pacemaker implantation rate at 30 days and new-onset atrial fibrillation (AF))
- Evaluation of the VARC-2¹⁹ defined event rates at 30 days from the index procedure.
 - Vascular access site complication (major and minor)
 - Bleeding (life-threatening, major and minor)
 - Acute kidney injury

- Prosthetic valve function at 30 days, 1 year and annually through 5 years post implant. (Includes prosthetic valve stenosis and prosthetic valve regurgitation).
- Clinical benefit endpoints at 30 days, 1 year and annually through 5 years post implant (if available)
 - NYHA functional classification
 - 6 Minute Walk Test (6MWT)
 - Quality of life measured with EQ-5D questionnaire through 1 year post-implant
- Evaluation of the TAVI-related resource utilization through hospital discharge (e.g. index procedural hospital/physician resources)
- Interim reporting at 30 days and 1-year all-cause mortality data may be performed on a subset of patients and compared with an appropriate external comparator. The results will be presented to appropriate agencies in France and in other countries where it will be deemed necessary for reimbursement purposes.

NOTE: Should new VARC or ESC Guidelines be published, endpoint analysis would be adjusted accordingly and analyzed to the extent that the previously gathered data supports the analyses based on the most current guidelines.

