Frailty assessment (NAP for Cohort B)	
Patient Frailty index will be assessed at baseline, at 30 days and at 1 Year. Frailty is a risk factor not included in the current surgical risk assessment tools. Frailty Index assessment will include:
 
 - 5 meters walking time - Grip strength - Wasting and malnutrition parameters (including weight loss, BMI and Serum albumin value to be obtained via blood sample)

Study activities	Definitions
	
- Cognitive impairment or dementia as measured with the mini-mental state examination (MMSE).
 
For further details/instructions, please refer to Appendix F: Frailty Assessment.

Blood sample (NAP for Cohort B)
	
 • Albumin: see frailty assessment • Hemoglobin, Creatinine (if available) • Troponin: at Enrollment/Baseline and between day 2 and 4 Post-implant or at discharge whatever occurs first.

Physical assessment (From 2Y visit onward for Cohort B)
	
At the baseline visit the following measurement must be assessed:
 
 • Height • Weight • Systolic/Diastolic blood pressure 
The following measurements must be assessed at all visits:
 
 • Weight • Systolic/Diastolic blood pressure

12 Leads ECG (NAP for Cohort B)
	
Assessment of dominant rhythm, heart rate, PR interval, QRS duration, bundle branch block, fascicular block etc.
 
The ECG is to be performed at baseline, within 24 hours Post-implant, at hospital discharge but no later than 7 days Post-implant, whatever occurs first and at 30days and 1 Year.

Medication assessment (From 2Y visit onward for Cohort B)
	
The following information on medication will be collected at each visit:
 
 • Beta Blockers • Calcium Channel Blockers • Anticoagulants • Antiplatelet agents including Aspirin • Diuretics • Ace-Inhibitors • Angiotensin Receptor Blocker (ARBs) • Statins 
At the implant visit the prophylactic antibiotics regimen will also be collected

Echocardiogram (From 2Y visit onward for Cohort B)
	
Each site will be responsible for performing and interpreting the baseline & post-implant and follow-up echocardiograms using the VARC 2 definitions.
 
For further details on echocardiographic variables, please refer to Appendix D: VARC 2 Endpoints Definitions.

Study activities	Definitions

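### Conduction disturbance and arrhythmia are reported yearly to 5 years on one curve, but no ECG is scheduled after 1 year (none in this study for Cohort B), so the late part is biased low

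*Combined protocol and SAP*

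**What the plan says.** **Endpoint and times.** Section 5.3.2 opens a list of "defined event rates at 30 days, 1 year and annually through 5 years post implant" and includes in it "New or worsened conduction disturbances and cardiac arrhythmias (including pacemaker implantation rate at 30 days and new-onset atrial fibrillation (AF". Within that item, only the pacemaker rate is tied to 30 days. The Synopsis (Section 2) lists the same endpoint as a separate bullet, with no time points other than 30 days for the pacemaker rate.

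**Analysis.** Section 9.4: "All safety secondary endpoints will be estimated using non-parametric survival analysis", and "All safety secondary endpoints will be reported at 30 days, 1 year, 2 years, 3 years, 4 years and 5 years post implant". Time runs from implant to first event, "or to the last documented contact date for the patients without the event". Both cohorts are analysed and shown separately.

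**Detection.** Section 6.2, Table 3, describes the ECG as assessing rhythm, PR interval, QRS duration and bundle branch or fascicular block. It is due at baseline, within 24 hours of implant, at discharge (by day 7), "whatever occurs first and at 30days and 1 Year". The Table 3 entry is marked "12 Leads ECG (NAP for Cohort B". Table 2 agrees, and the visit lists for years 2 to 5 (6.2.7 to 6.2.10) contain no ECG. The Summary of changes (Modification 15) shows that removing the later ECGs was deliberate.

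**Other routes.** Section 7.3.2 requires reporting of all serious adverse events and of non-serious cardiovascular events, whatever their relation to the device. Section 6.2.11 requires an ECG done at an unscheduled visit to be documented.

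**The concern.** The endpoint includes findings that can be silent, such as bundle branch block, lower-grade AV block and AF without symptoms. Up to 1 year, Cohort A patients have scheduled ECGs that can show them. After 1 year nothing scheduled takes the ECG's place: the physical assessment at follow-up consists of weight and blood pressure, and a referring physician may conduct the visit. A patient with a new silent finding in year 3 therefore stays in the risk set as event-free until last contact.

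The curve then tends to flatten after 1 year partly because detection becomes less intense. Section 4 describes the valve as designed to limit damage to the conduction system, and Sections 9.5 and 10 foresee use of the data for reimbursement and market approval. A plateau that comes from the visit schedule could be taken as evidence of late conduction safety.

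**Working it through.** The plan states no rate, precision or sample size for this endpoint, so there is no figure to reproduce. The check sets the reporting times against the ECG schedule and then illustrates the possible bias.

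**Step 1. Reporting times against scheduled ECGs**

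| Time | Reported (9.4) | ECG, Cohort A | ECG in this study, Cohort B |
|---|---|---|---|
| 30 days | yes | yes | no |
| 1 year | yes | yes | no |
| 2, 3, 4, 5 years | yes | no | no |

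Four of the six reporting times have no scheduled ECG in Cohort A.

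**Step 2. Planned follow-up after the last scheduled ECG, Cohort A.** Inputs are the 1-year visit at day 365 ± 90 (6.2.6) and the 5-year visit at day 1825 (6.2.10).
- On time: 1825 − 365 = 1460 days; 1460/1825 = 80%.
- Earliest 1-year visit, day 275: 1825 − 275 = 1550 days; 85%.
- Latest, day 455: 1825 − 455 = 1370 days; 75%.

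For Cohort B the share is 100% of its time in this study (up to 4 years). Data to 1 year sit in the parent trials and are not collected again (6.1.2, 6.2.1).

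These shares describe the schedule and are not a measure of bias. Year 1 is not continuously observed either, since no ECG is scheduled between 30 days and 1 year. The step at 1 year is from occasional scheduled checks to none.

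**Step 3. Illustration of size.** All three inputs are assumptions; the documents give none of them.
- F1: cumulative incidence at 1 year, 20% to 30%.
- λ: true yearly hazard of a new event after 1 year, 2% to 8%.
- s: share of later events that only an ECG would show and that are never found otherwise, 25% to 75%.

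True 5-year incidence = 1 − (1 − F1)·exp(−4λ). 
Observed = 1 − (1 − F1)·exp(−4λ(1 − s)).

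| F1 | λ | s | True | Observed | Gap (points, unrounded inputs) |
|---|---|---|---|---|---|
| 30% | 2% | 25% | 35.4% | 34.1% | 1.3 (smallest) |
| 20% | 5% | 25% | 34.5% | 31.1% | 3.4 |
| 20% | 5% | 50% | 34.5% | 27.6% | 6.9 |
| 20% | 5% | 75% | 34.5% | 23.9% | 10.6 |
| 20% | 8% | 75% | 41.9% | 26.2% | 15.8 (largest) |

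Middle row: 1 − 0.80·exp(−0.20) = 0.345 and 1 − 0.80·exp(−0.10) = 0.276.

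Among patients event-free at 1 year, the observed share of the true year 1 to 5 incidence is [1 − exp(−4λ(1 − s))]/[1 − exp(−4λ)], which runs from about 0.26 to 0.78 over the grid. It follows 1 − s closely, so the assumption about silent events largely fixes the answer.

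**The case against.** **Late events are still captured.** Cardiovascular adverse events are reportable throughout, every yearly visit includes adverse event, medication and echocardiographic assessment, and unscheduled ECGs are documented, in Cohort B as well. This stands. A reader might infer that arrhythmias after 1 year cannot be recorded; the documents do not support that. What is lost is the systematic search for silent findings. Some of these will surface later as symptoms, pacemakers or incidental findings and so be delayed rather than missed, which makes the illustration lean towards a larger gap.

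**The endpoint is not defined as ECG-based.** Section 5.3.2 points to Appendix D, which has no entry for conduction disturbance or arrhythmia. Events are adjudicated under a charter that is not among the documents. A reader might infer that the definition changes at 1 year; the text does not show this. Even if the endpoint rests on adverse event reports throughout, scheduled ECGs before 1 year can prompt such reports and later ones cannot. Detection intensity still drops.

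**The yearly times are unclear.** The Synopsis gives none, and the general sentence in 9.4 also takes in bleeding, kidney and vascular events that 5.3.2 limits to 30 days. That is a fair point and a reason to reconcile the three places. Section 5.3.2 nonetheless lists this endpoint under yearly reporting.

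**A separate analysis plan may deal with it.** Section 9.4 defers only other secondary endpoints to that plan and itself fixes times and censoring for all the safety ones.

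**The endpoint is secondary and descriptive**, in an uncontrolled study without a success criterion. This limits the importance of the point but does not remove the bias.

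**Conclusion.** The point holds. As written, the plan gives one curve in which detection weakens at 1 year while the risk set carries on to last contact. The part after 1 year is biased low and cannot be compared directly with the 30-day and 1-year part. The direction rests on one assumption: that some new, clinically silent events occur after 1 year. In Cohort B, all follow-up in this study is without scheduled ECGs, although the parent trials may hold earlier ones.

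The documents establish the extent of the mismatch (80% of planned Cohort A days, four of six reporting times) but not the size of the bias. The 1.3 to 15.8 percentage points above are illustrative. A reader might take the schedule shares as a diluted person-time denominator, but Kaplan-Meier works with patients at risk and has no such denominator. The primary endpoint, the 30-day pacemaker rate and the Cohort A 30-day and 1-year results are unaffected.

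**What to change.** 1. Reconcile the Synopsis, 5.3.2 and 9.4 on the reporting times for this endpoint, and state whether a silent ECG finding counts as an event, since Appendix D does not say.
2. Report the ECG-supported endpoint (all conduction disturbance and new-onset AF) in Cohort A at 30 days and 1 year only. Count findings from the 1-year visit ECG when it falls within its window, and give the number of patients with an ECG at each time.
3. Do not censor event-free patients at their last ECG. With the ±90-day window, those seen on days 275 to 364 would leave the risk set before day 365, and those without a 1-year ECG would go back to about day 30. If events found between ECGs still counted, the 1-year rate would be pushed up.
4. For years 2 to 5, and for Cohort B in this study, report permanent pacemaker implantation and arrhythmia or AV block recorded as adverse events. Show these as a separate endpoint labelled clinically detected, not joined to the ECG-supported curve.

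The cost is protocol and analysis-plan wording and one extra table, with no new ECGs or visits. The downside is that no ECG-based rate can be quoted beyond 1 year.
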